#### 6.5.2.9 Proteinuria

Proteinuria is an anticipated AE with the inhibition of VEGF pathways and has been observed in cabozantinib clinical studies. Nephrotic syndrome has been reported with cabozantinib and other inhibitors of VEGF pathways.

During each safety assessment visit, proteinuria will be quantified by measuring the urine protein-to-creatinine (UPCR) ratio performed by the central lab. In addition, urine dipstick analysis performed by the local lab will be done at least every 8 weeks and as clinically indicated.

Management of proteinuria will be based on UPCR results provided by the central laboratory (see Table 6-10). However, since dipstick results from the local labs may be available prior to the UPCR results from the central laboratory, they can be used by the investigator for interim management. If the dipstick analysis shows proteinuria  $\geq 3+$ , the investigator may decide to

interrupt cabozantinib dosing until the UPCR result becomes and available and treatment decisions can be made.

Table 6-10: Guidelines for the Management of Treatment Emergent Proteinuria

Severity of Proteinuria (UPCR)	Action To Be Taken
≤ 1 mg/mg (≤ 113.1 mg/mmol)	No change in study treatment or monitoring
> 1 and < 2.0 mg/mg (> 113.1 and < 226.2 mg/mmol)	
 
No change in study treatment required
 
Consider confirming with a 24-hour protein excretion within 7 days
 
Repeat UPCR within 7 days and once every week as clinically indicated. If UPCR is < 1 mg/mg on two consecutive readings, then UPCR monitoring can revert to protocol-specific time points. (Second reading is a confirmatory reading and can be done within 1 week of the first reading.) If UPCR remains > 1 and < 2 for 1 month, check urine protein/creatinine per protocol or as clinically indicated.
 

≥ 2.0 mg/mg (≥ 226.2 mg/mmol)	
 
Hold study treatment pending repeat UPCR within 7 days and/or 24-hour urine protein.
 
If ≥ 2.0 mg/mg on repeat UPCR or ≥ 2 g/24 hours on 24-hour urine collection, continue to hold study treatment and check UPCR every 7 days as clinically indicated. If UPCR decreases to < 2 mg/mg, restart study treatment at a reduced dose and monitoring of urine protein/creatinine should continue once every week as clinically indicated until the UPCR decreases to < 1 mg/mg or is determined to be stable (< 20% change) for 1 month at which point monitoring of UPCR can be per protocol or as clinically indicated.
 
If UPCR remains ≥ 2 and stable (< 20% change) for 1 month, can revert to monitoring per protocol or as clinically indicated. Continue to hold treatment until UPCR < 2.
 

Nephrotic syndrome	Discontinue all study treatment

UPCR, urine protein/creatinine ratio.

# 6.5.2.10 Corrected QTc Prolongation

The effect of orally administered cabozantinib at 140 mg/day (FBE) on QTc interval was evaluated in a randomized, double-blinded, placebo-controlled Phase 3 study in subjects with MTC. A mean increase in QT interval corrected by Fridericia (QTcF) of 10-15 ms was observed at 4 weeks after initiating cabozantinib. A concentration-QTc relationship could not be

<sup>a Study treatment includes both cabozantinib and matched placebo.

definitively established. Changes in cardiac wave form morphology or new rhythms were not observed. Thus far no cabozantinib-treated subjects have had a treatment-emergent QTcF > 500 ms. Accordingly, subjects in this study will be monitored for potential QT effects.

Only subjects with a baseline QTcF interval corrected by Fridericia (QTcF)  $\leq$  500 ms are eligible for this study. Subjects will have ECGs performed at times designated by the protocol (Section 5.5.4 and Appendix A).

If at any time on study there is an increase in QTcF interval to an absolute value > 500 ms or an increase of >60 ms above baseline, two additional ECGs must be performed with intervals not less than 3 min apart within 30 min after the initial ECG.

If the average QTcF from the three ECGs is > 500 ms or an increase >60 ms above baseline, the following actions must be taken:

- Withhold study treatment
- Immediately notify the Sponsor
- Hospitalize symptomatic subjects (eg, with palpitations, dizziness, syncope, orthostatic hypotension, a significant ventricular arrhythmia on ECG) for a thorough cardiology evaluation and treatment according to standard clinical practice
- Consider cardiology consultation for asymptomatic subjects for evaluation and management
- Check electrolytes, especially magnesium, potassium, and calcium; correct abnormalities as clinically indicated
- Check concomitant medications for any medication that may have contributed to QTc prolongation, and if possible, discontinue these medications (see http://www.qtdrugs.org)
- Send ECGs to central ECG laboratory (see ECG study manual)
- Repeat ECG triplicates hourly until the average QTcF is  $\leq$  500 ms or an increase of  $\leq$  60 ms above baseline, or otherwise determined by consultation with a cardiologist

Subjects with QTc prolongation and symptoms must be monitored closely until the QTc elevation and symptoms have resolved. Study treatment may be restarted at a reduced dose level if all of the following conditions are met:

- Symptoms are determined to be unrelated to the QT interval prolongation
- The QTcF value > 500 ms or the increase >60 ms above baseline is not confirmed by the central ECG laboratory or a QTcF > 500 ms or an increase >60 ms above baseline confirmed by the central laboratory returns to ≤ 500 ms or decreased to <60 ms above baseline and a reversible cause has been identified and treated.
- Study treatment has been interrupted through a minimum of 1 week following the return of the QTcF to ≤ 500 ms or a decrease to <60 ms above baseline

• Sponsor has reviewed all available information and has agreed to the continuation of study treatment

Following reinitiation of study treatment, ECGs must be repeated weekly for 2 weeks, then every 2 weeks for 1 month, then according to the protocol-defined time points.

Study treatment must be permanently discontinued if either of the following applies:

- Cardiac evaluation confirms that symptoms are the consequence of QT interval prolongation
- Recurrence of QTcF prolongation (confirmed by central ECG lab) after reinitiation of study treatment at a reduced dose

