# 5.5.4 Electrocardiogram (ECG) Assessments

Standard 12-lead equipment will be used for all ECGs.

The Fridericia formula is depicted below for calculation of QTcF.

$$QTcF = \frac{QT}{RR^{1/3}}$$

QT = measured QT interval in milliseconds; RR = measured R to R interval (which can be derived from the heart rate [HR] as 60/HR)

ECGs to establish eligibility must be done within 28 days prior to randomization (Appendix A). To confirm suitability for treatment after randomization, ECGs must be repeated on W1D1 prior to administering the first dose of study treatment unless screening tests were performed within 14 days prior to W1D1.

At screening, if the initial QTcF is > 500 ms, a total of 3 ECGs each separated by at least 3 minutes should be performed. If the average of these three consecutive results for QTcF is  $\leq 500$  ms, the subject meets eligibility in this regard.

During the study, single ECG assessments will be performed as indicated in Appendix A. If cardiac abnormalities are detected or suspected, two additional ECGs must be performed at intervals at least 3 minutes apart in order to confirm the finding. If at any time while on study there is an increase in average QTcF > 500 ms or an increase >60 ms above baseline, study treatment must be immediately interrupted and instructions in Section 6.5.2.10 for continued monitoring of QTc must be followed.

Abnormalities in the ECG that lead to a change in subject management (eg, dose reduced or withheld, treatment discontinued, requiring additional medication or monitoring), or that result in clinical symptoms are considered clinically significant for the purposes of this study and should be reported as AEs by the investigator. If values meet criteria defining them as serious, they must be reported as SAEs (Section 8.2).

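### Section 6.5.2.10 holds drug when either QTcF limit is exceeded, but also lets hourly ECGs stop, and in one case the 1-week restart clock start, when only one limit is met

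*Protocol*

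**What the plan says.** **Hold rule.** Section 6.5.2.10 lists mandatory actions, starting with withholding study treatment, "If the average QTcF from the three ECGs is > 500 ms or an increase >60 ms above baseline". Section 5.5.4 states the same trigger ("If at any time while on study there is an increase in average QTcF > 500 ms or an increase >60 ms above baseline") and requires immediate interruption.

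**Hourly ECGs.** One of those actions is "Repeat ECG triplicates hourly until the average QTcF is" ≤ 500 ms or the increase is ≤ 60 ms above baseline, unless consultation with a cardiologist determines otherwise.

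**Restart.** Treatment may resume at a reduced dose only if every listed condition is met. Two conditions use the QTcF limits:
- The prolongation is not confirmed by the central ECG laboratory, or a confirmed value "returns to ≤ 500 ms or decreased to <60 ms above baseline" and a reversible cause has been found and treated.
- At least 1 week of interruption has passed "following the return of the QTcF to ≤ 500 ms or a decrease to <60 ms above baseline".

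The other conditions are that symptoms are judged unrelated to the QT prolongation and that "Sponsor has reviewed all available information and has agreed to the continuation of study treatment".

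**Experience so far.** The same section reports: "Thus far no cabozantinib-treated subjects have had a treatment-emergent QTcF > 500 ms".

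**The concern.** If either of two limits triggers a hold, the trigger has cleared only when neither is exceeded. All three release clauses in Section 6.5.2.10 instead join the limits with *or*, so a release can be reached while the hold rule is still met.

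Two things are at stake. Hourly triplicate ECGs could end early, or literally never be required, in a subject whose drug has just been withheld for QTc prolongation. The 1-week interval before restart could also begin while QTcF still breaches a limit.

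The 60 ms boundary is also inconsistent: ≤ 60 ms ends the hourly ECGs, but the restart bullets ask for < 60 ms.

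**Working it through.** The plan gives no figure to reproduce. The check is on the logic of the rules. Let *b* be baseline QTcF and *q* the current average, in whole ms.

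**Rules as written**
- Hold (5.5.4 and 6.5.2.10): *q* > 500 or *q* − *b* > 60, that is, *q* > min(500, *b* + 60).
- Hourly stop (6.5.2.10): *q* ≤ 500 or *q* − *b* ≤ 60, that is, *q* ≤ max(500, *b* + 60). The clause describes a state; it does not say that the value must have returned.
- Restart (6.5.2.10): the value has returned to ≤ 500, or has decreased to < 60 above baseline. Each verb presupposes an earlier breach of that same limit.

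**1. Hourly ECGs.** Hold and stop are both true for min(500, *b* + 60) < *q* ≤ max(500, *b* + 60), a band of |440 − *b*| ms.

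| Baseline | Hold above | Stop at or below | Readings both held and stopped |
|---|---|---|---|
| 400 | 460 | 500 | 461–500 |
| 420 | 480 | 500 | 481–500 |
| 430 | 490 | 500 | 491–500 |
| 440 | 500 | 500 | none |
| 450 | 500 | 510 | 501–510 |
| 460 | 500 | 520 | 501–520 |

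A reading in this band exceeds exactly one limit, so every single-limit breach satisfies the stop at the reading that caused the hold. A reading that exceeds both limits does not, but it does once one limit recovers. Enumeration over baselines 350–500 and readings 350–619 agrees: all 5,925 single-limit hold readings meet the stop, and none of the 16,139 both-limit readings do. These count grid cells, not patients.

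A hold with *q* ≤ 500 needs 500 − *b* > 60, so *b* ≤ 439. If the reported absence of treatment-emergent values above 500 ms continues, every hold comes from the 60 ms limit in such a subject, and each one literally meets the hourly stop at once.

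**2. Restart, one limit breached.** The clock can start only through the limit that was breached. The other limit was not exceeded at the peak, and is not exceeded at any later reading at or below the peak. So when the clock starts, the hold rule is no longer met. Enumeration found no failing case.

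**3. Restart, both limits breached, one recovered.**
- *b* = 430, peak 510 (+80), now 495 (+65): returned to ≤ 500, but 65 > 60, so the hold rule is still met.
- *b* = 460, peak 530 (+70), now 510 (+50): decreased to < 60, but 510 > 500, so the hold rule is still met.

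In both cases the 1-week clock can start. The central-confirmation bullet has the same gap.

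**4. With *and*.** Release when *q* ≤ 500 and *q* − *b* ≤ 60, that is, *q* ≤ min(500, *b* + 60). This is the exact complement of the hold rule, so no value satisfies both.

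**The case against.** The strongest reply is that nobody would read the hourly bullet this way. It is a mandatory action after a breach, and the literal reading would leave it with nothing to do after any single-limit breach. Trigger and stop list the same two limits in the same order, so a site would naturally pair each stop limit with its own trigger. The protocol is also loose with these words elsewhere. Table 6-9 joins the blood pressure limits with *and* for re-escalation, but uses *or* for the same kind of pair in other rows.

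Part of this stands. The paired reading is plausible and probably intended, and the blood pressure table does not settle the meaning here. But the text does not state the pairing, and pairing does not say what to do for a subject who breached both limits and recovered on one.

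A second reply is that other protections cover the risk:
- A cardiologist can set a different stopping point for the hourly ECGs. Symptomatic subjects are hospitalized and "must be monitored closely until the QTc elevation and symptoms have resolved". Cardiology consultation is to be considered for those without symptoms.
- Section 5.4 asks for unscheduled visits, weekly or more often as clinically indicated, while drug is held.
- All restart conditions must be met. ECGs are then repeated weekly for 2 weeks and every 2 weeks for 1 month, and centrally confirmed recurrence means permanent discontinuation.

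This stands and limits the harm, but it does not correct the bullet. In subjects without symptoms, the hourly bullet is the specific acute ECG instruction.

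A third reply is that past absence of values above 500 ms does not guarantee that future holds all come from the 60 ms limit, because site readings can trigger a hold before central review. That is fair, and the statement above is conditional for that reason. A site-read hold above 500 ms that breaches that limit alone still falls in the overlap.

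**Conclusion.** The concern holds and is minor. On its literal wording, the hourly-ECG bullet is met at the triggering reading for every single-limit breach, over a band of |440 − baseline| ms. The restart bullets are correct for a single-limit breach and leave a gap only for a subject who breached both limits and has recovered on one.

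This rests on reading the hourly bullet as a state, and on reading the restart verbs as requiring an earlier breach of the same limit. Under the paired reading of the hourly bullet, only the both-limits case remains unresolved. The documents give no frequency for either kind of breach on the triplicate average, so the number of subjects affected cannot be estimated.

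The consequence is limited to an early end of hourly ECGs and, in the both-limits case, an early start of the 1-week clock. Neither leads to dosing by itself, because the hold rule applies at any time on study and restart needs all the other conditions. There is no effect on PFS, power or type I error.

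**What to change.** In Section 6.5.2.10, change three clauses (the hourly-ECG bullet, the central-confirmation restart bullet and the 1-week restart bullet) so that each requires average QTcF ≤ 500 ms **and** an increase of ≤ 60 ms above baseline. Using ≤ 60 ms in all three removes the boundary mismatch and makes release the exact complement of the hold. Keep the cardiologist exception in the hourly bullet and every other restart condition. Section 5.5.4 states only the hold rule and needs no change.

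The cost is the wording of three bullets. Because it alters when required ECGs end and when the restart interval begins, it may need IRB/EC submission under Section 14 rather than a clarification letter alone. It can go with the next amendment. Compared with the paired reading, it adds no hourly ECGs after a single-limit breach as long as the other limit stays unbreached. After a double breach they may run longer, and the cardiologist exception can cap that. Design, sample size and analysis do not change.

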During the Maintenance Phase no data are to be entered into electronic case report forms. Study central laboratory samples are not to be obtained. Do not submit local laboratory results to the study local laboratory management vendor, radiographic images to the study central imaging vendor, or ECGs to the study central cardiac safety vendor.

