Study drug accountability is to continue as described in Section 6.4.

To receive study treatment supplies it may be necessary for subjects to visit the study site more frequently than clinic visits for safety and tumor evaluations performed per standard of care.

Site monitoring visits will occur at a reduced frequency to ensure adherence to GCP, protocol compliance, adequate subject safety follow-up, study drug accountability, and reporting of SAEs and other reportable events.

During the Maintenance Phase no data are to be entered into electronic case report forms. Study central laboratory samples are not to be obtained. Do not submit local laboratory results to the study local laboratory management vendor, radiographic images to the study central imaging vendor, or ECGs to the study central cardiac safety vendor.

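### In the Maintenance Phase, the permanent stop for recurrent QTcF prolongation needs a central ECG reading, but sites are told not to submit ECGs: a small, rare gap that one sentence closes

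*Protocol*

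**What the plan says.** Protocol Section 6.5.2.10 applies throughout the study. When the average of three ECGs shows QTcF above 500 ms, or more than 60 ms above baseline, a list of mandatory actions follows. It includes withholding treatment, notifying the Sponsor at once and sending the tracings to the central ECG laboratory.

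Restart at a reduced dose needs all of four conditions. The second can be met in two ways: the crossing "is not confirmed by the central ECG laboratory", or a crossing "confirmed by the central laboratory returns to" within limits after a reversible cause has been found and treated. The fourth is that the "Sponsor has reviewed all available information and has agreed to the continuation of study treatment".

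There are two QT-specific permanent stops. One is for symptoms that cardiac evaluation attributes to QT prolongation. The other is "Recurrence of QTcF prolongation (confirmed by central ECG lab) after reinitiation of study treatment at a reduced dose".

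Section 3.5.3 makes the events in Section 6.5.2 reasons for discontinuation, and Section 5.2.1 keeps the discontinuation criteria in force in the Maintenance Phase. For that phase Section 5.2.1 also says "During the Maintenance Phase no data are to be entered into electronic case report forms", and lists what sites are not to submit, ending with "radiographic images to the study central imaging vendor, or ECGs to the study central cardiac safety vendor". Appendix B repeats this in its text and in its table note: "Do not submit local laboratory results to the study local laboratory management vendor, radiographic images to the study central imaging vendor, or ECGs". None of the three places states an exception.

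**The concern.** A mandatory stop that depends on an outside confirmation works only if the confirmation can be obtained. Section 6.5.2.10 sends triggered ECGs to a central reader and waits for the answer. The Maintenance Phase text appears to close that route and names nothing in its place. Subjects in that phase are still taking active drug, some at 140 mg, the dose at which Section 6.5.2.10 reports a mean QTcF increase of 10 to 15 ms at 4 weeks. The frequency of assessments moves to standard of care, so site staff would rely on the written rules when a crossing occurs. What is at stake is whether one cardiac stopping rule can be carried out as written. The efficacy and safety results of the trial are not at stake.

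**Working it through.** There is no figure to reproduce. The check sets the texts side by side.

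1. **Does the QT rule reach the Maintenance Phase?** Yes. Sections 5.5.4 and 6.5.2.10 set no phase limit. Section 5.2.1 continues treatment until a discontinuation criterion is met, and Section 3.5.3 counts the Section 6.5.2 events among those criteria.

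2. **What does the rule need from a central reader?** The mandatory action list requires the ECGs to be sent. Of the 2 permanent-stop criteria, 1 depends on central confirmation. It is the only QT-specific stop that covers a recurrence without QT-related symptoms. Within the second restart condition, 2 of 2 branches refer to the central reading.

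3. **Can sites obtain that reading in the Maintenance Phase?** Not if the instruction in Section 5.2.1 and Appendix B governs and the central ECG laboratory is the central cardiac safety vendor. The protocol does not equate the names, but it describes no other central ECG reader. SAP Section 8.8 names one review besides the investigator's, which fits a single reader but does not prove it.

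4. **Is a substitute named?** For laboratory tests, yes: Section 5.5.5 says central testing ends in this phase and local tests under standard of care take over. No matching sentence exists for ECG confirmation. The safety row of the Appendix B table names only clinical examination and local laboratory work.

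5. **What happens to a subject who recurs?** The clearest case is a subject whose first crossing was read centrally, who restarted before the Maintenance Phase, and who crosses again within it without QT-related symptoms.
   - Treatment is withheld and the Sponsor is notified. Neither step needs a central reading.
   - The permanent stop is not triggered as written, because no central confirmation exists.
   - The restart rule has two readings. If the absence of a reading counts as not confirmed, the second condition is met and the other three decide. If it counts as not assessable, the condition fails and restart is not authorised. The second reading is the safer one.
   - If the hold lasts more than 6 weeks, Section 3.5.3 makes that a reason to discontinue unless the Sponsor approves continuation.

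6. **What else remains without a central reading?** Section 3.5.3 keeps discontinuation at the Sponsor's request, for unacceptable side effects in the investigator's view, and when the investigator judges that continuing is not in the subject's interest. The stop for symptoms caused by QT prolongation also stands. AEs that lead to a hold or reduction are still reported (Section 5.2.1).

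**The case against.** The strongest reply is that the Maintenance Phase instruction concerns routine data flow. In Section 5.2.1 it follows the end of eCRF entry and covers laboratory results and images as well as ECGs. A specific, event-triggered safety rule would usually be taken to prevail over a general end-of-collection instruction. The two names may also denote different bodies, in which case there is no conflict, and the ECG study manual cited in Section 6.5.2.10 could settle either point. This reading is plausible, and it limits the weight of the concern. It does not remove it: the instruction appears three times without an exception, and a site should not have to infer one.

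A reader might go further and infer that a subject with a recurrence would be allowed a further restart at the next lower dose that the permanent stop would have ruled out. The documents do not support any such count. Sponsor agreement is an additional restart condition and does not replace the second one, and on the safer reading of that condition restart is not authorised at all. Nor do the documents support an inference that subjects are left unprotected, given the hold, the notification and the Sponsor and investigator stops.

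**Conclusion.** The inconsistency is real and minor. It rests on three assumptions: that the central ECG laboratory and the central cardiac safety vendor are the same reader, that the Maintenance Phase instruction governs, and that the ECG manual, which is not among the documents, holds no exception. On these, 1 of the 2 QT-specific permanent stops cannot be triggered as written in that phase, and one restart condition is ambiguous. In place of an unconditional stop, the subject is on hold, and the outcome depends on how the restart condition is read, on the Sponsor and investigator decisions, and on a 6-week limit that the Sponsor may waive.

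The case should be rare. Section 6.5.2.10 reports no treatment-emergent QTcF above 500 ms so far. That supports rarity for this trigger only: the documents give neither the frequency of rises above 60 ms nor the number of subjects expected in the Maintenance Phase, so no rate can be calculated. The trial's conclusions are unaffected, because SAP Section 2.4 excludes Maintenance Phase data from the CSR.

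**What to change.** Add one sentence to Section 5.2.1 and to Appendix B, next to the instruction not to submit: *ECGs that meet the triggers in Section 6.5.2.10 are exempt and still go to the central ECG laboratory.* This restores both the stop and the restart condition without changing any QTcF limit.

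The cost is one sentence in a protocol amendment and an occasional triggered ECG read by the vendor.

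Letting the local triplicate average serve as the confirmation in this phase would not be a sound alternative. That average is already the trigger, so every trigger would confirm itself. The not-confirmed restart branch could never be met, and an erroneous local reading at recurrence could end treatment permanently.
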